9.4 Efficacy Evaluations

The primary efficacy variable is change from Baseline to Week 6/Week 24 in WSRS score. Summary statistics (mean, SD, minimum, median, maximum) and 95% confidence interval (CI) will be presented for the changes scores for each treatment and for the difference in change scores between the two treatment groups (Comparator minus Test product, i.e., Restylane minus Revanesse). The 95% CI for difference between treatments will be constructed assuming a normal distribution of the change scores. If the upper bound of this 95% CI is less than the pre-specified non-inferiority (NI) limit (i.e. 0.50), the Test product will be claimed to be non-inferior to the Comparator product.

Secondary efficacy endpoints include the responder rate, i.e., the percentage of subjects with treatment success (defined as at least a 1-grade improvement in WSRS from baseline to Week 24), pGAI score at Visit 6/Week 24, and iGAI score at Visit 6/Week 24. For these secondary variables, the null hypothesis to be tested is that there is no difference between the two products. The variables responder rate, pGAI and iGAI scores at Visit 6/Week 24 will be tabulated with frequencies and percentage and analyzed using the Wilcoxon matched-pairs signed rank test.

Other efficacy variables include change in WSRS score, pGAI, and iGAI at Visit 2/Week 1, Visit 3/Week 2, Visit 4/Week 4, and Visit 5/Week 12. Treatment difference with respect to these variables will be examined using descriptive summaries.

All efficacy analyses will be performed for both the PP and mITT populations. For the primary endpoint, the results from PP are considered definitive and those from mITT supportive.

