Test product: Revanesse Ultra: a clear, colorless gel in 1.0 mL pre-filled syringes with 25 mg/mL of stabilized hyaluronic acid.

Comparator product: Restylane: a clear, colorless gel in 1.0 mL pre-filled syringes with 20 mg/mL of stabilized hyaluronic acid.

The injection will be given intradermally and for best results should be injected in the mid-dermis.

Statistical Methods:

Sample Size Determination: Approximately 63 per-protocol (PP) subjects will supply a power of 85% with respect to change from baseline to Month 6 in WSRS score based on the following:

- The non-inferiority limit is 0.50. If the upper bound of the 95% confidence interval (CI) treatment difference (Comparator – Test) is less than 0.50 for the PP population, the Test product will be claimed to be non-inferior to the Comparator product.
- The difference between Comparator and Test (i.e., Comparator – Test) has a mean value of 0, with a standard deviation of 1.30.

A total of 163 subjects will be randomized in the study to provide adequate data for monitoring safety of the study product.

Analysis Populations:

Intent-to-treat (ITT) (safety) population: All randomized subjects who received study product.

Modified intent-to-treat (mITT): All randomized subjects who met the inclusion/exclusion criteria, were randomized, received both study products, and returned for at least 1 post-injection assessment of WSRS score from both sides of the face.

Per-protocol (PP): All randomized subjects who met all inclusion/exclusion criteria; received both study products; completed Visit 6/Week 24 within the specified window, had data on WSRS score from both sides of the face, and had no significant protocol violations that would affect the treatment evaluation.

Efficacy analyses will be performed on the mITT and PP populations. Safety analyses will be performed on the ITT population.

Efficacy Analysis:

The primary efficacy variable is change from Baseline to Visit 6/Week 24 in WSRS score. Summary statistics (mean, SD, minimum, median, maximum) and 95% CI will be presented for the changes scores for each treatment and for the difference in change scores between the two treatment groups (Comparator minus Test). The 95% CI for the difference between

treatments will be constructed using the paired t-test. If the upper bound of this 95% CI is less than the pre-specified non-inferiority limit (i.e. 0.50), the Test product will be claimed to be non-inferior to the Comparator product.

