8 INVESTIGATIONAL PLAN

8.1 Overall Study Design

This is a randomized, multicenter, double-blind, split-face study in subjects seeking NLF correction. Subjects will be treated with Revanesse Ultra in the NLF on one side of the face and Restylane in the NLF on the other side of the face. The side of the face for each product will be randomly assigned. The investigator performing the evaluations and the subject will be blinded to the treatment; injections of the study product will be performed by an unblinded injecting investigator.

Approximately 163 subjects will be randomized at approximately 5 study sites in the United States (US).

At each visit, investigator and subject evaluations of the treated areas will be performed and recorded. Visits will occur at:

- Visit 1/Week 0 (Day 1) – baseline and treatment
- Visit 2/Week 1 (\pm 2 days) – interim visit, touch-up if the iGAI score = 3 or 4
- Visit 3/Week 2 (\pm 2 days) – interim visit
- Visit 4/Week 4 (\pm 4 days) – interim visit
- Visit 5/Week 12 (\pm 4 days) – interim visit
- Visit 6/Week 24 (\pm 7 days) – optional open-label retreatment with Revanesse Ultra for subjects if their baseline WSRS scores have returned to baseline, or as needed to achieve optimal correction if their baseline WSRS scores have not returned to baseline; End of Study for subjects not being retreated
- Visit 7/Week 28 (\pm 7 days) – follow-up for retreated subjects
- Visit 8/Week 52 (\pm 7 days) – End of Study for retreated subjects

A telephone contact will also be performed at Week 40 (\pm 7 days) for retreated subjects to assess adverse events and concomitant medications.

Evaluations include Wrinkle Severity Rating Scale (WSRS), Patient Global Aesthetic Improvement (pGAI), and Investigator Global Aesthetic Improvement (iGAI). Safety will be assessed by monitoring adverse events (AEs) at all study visits. Other evaluations include the Patient Comfort Rating (PCR) and Investigator Ease of Use Assessment. A diary card will be dispensed to each enrolled subject at Visit 1/Day 1. The subject will be instructed to complete the diary card to record any AEs experienced for the first 2 weeks after treatment.

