8.4.2 Method of Treatment Assignment, Randomization, and/or Stratification

Every subject will receive Revanesse Ultra on one side of the face and Restylane on the other side of the face. The side of the face treated with either product will vary from subject to subject based on the randomization assignment made at Visit 1/Day 1.

Subjects who satisfy all of the inclusion and none of the exclusion criteria will be randomized with respect to which side of the face receives which treatment. Randomization will be performed according to a computer-generated randomization scheme. The randomization scheme will be generated and maintained by an independent third party. A sealed copy of the randomization scheme should be retained at each site and should be available to regulatory authorities at the time of site inspection to allow for verification of the treatment identity for each subject.

A unique subject number will be assigned to each subject. Each site will receive a list of randomization code numbers and corresponding study product boxes. Each eligible subject will be assigned a unique randomization code number in ascending order.

No stratification based on age, sex, or other characteristics will be performed.

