8.4.3 Administration of Dose for Each Subject

Subjects are physically masked (blindfolded) just prior to and during all injection procedures to prevent observation of the syringes containing study product.

Injections of the study product are performed by the unblinded injecting investigator. The blinded evaluator is not allowed to retrieve study supplies or to be present during opening of the study supplies or during the injections. The injecting investigator is not to have any discussion with the blinded evaluator or subjects regarding the treatments.

Up to a maximum of 2.0 mL (2 pre-filled syringes) will be used per treatment on each nasolabial fold similar to the comparator agent based on previous studies and common clinical practice.

The injection will be given intradermally and for best results should be injected in the mid-dermis. The treatment technique and the volume per treatment should be as similar as possible on both sides of the face.

For many patients with moderate NLFs, one syringe will be adequate per NLF. Based on the iGAI score at that time, a touch-up treatment may be administered at Visit 2/Week 1.

For this study, topical anesthetic will not be used. Ice may be applied before the treatment if the injecting investigator deems it necessary. The same technique should be used on both sides of the face. Using the nondominant hand to apply gentle downward traction to the inferiormost aspect of the fold to immobilize it, the dominant hand is used to inject filler. Steadying the injecting hand on the mandible or the other hand, the linear threading technique is most easily used to deposit the filler beneath the fold and efface it.

The peri-alar sulcus, a triangular shaped concavity at the upper end of the fold, may be more effectively filled with the fanning technique of implantation, where two or three threads are deposited in a fan-like array. Wide portions of the fold may require several threads placed side by side, with gentle massage after each thread is placed.

Treatment of this area is generally easy and straightforward. Notice that the fold is partially formed by prominent cheek tissue that is lateral to it, with the fold becoming more prominent as the cheek becomes more protuberant. Therefore, injections should stay medial to the fold to fill it. Injecting lateral to the fold, in the excessive cheek tissue, can actually tend to accentuate the fold.

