9.2 General Considerations

Two-sided hypothesis testing will be conducted for all tests. Resulting p-values less than 0.05 will be considered statistically significant unless noted otherwise. No adjustments of p-values for multiple comparisons will be made. SAS software (version 9.1.3) will be used for all data analyses and tabulations.

Missing efficacy data will be imputed via the last observation carried forward (LOCF) method in the mITT analysis. For the PP population, efficacy analysis will be performed using all the available data without imputation for the missing values.

For demographic and baseline characteristics and the safety profile, each variable will be analyzed using the existing data. Subjects with missing data will be excluded only from the analyses for which data are not available.

9.3 Comparability of Subjects at Baseline (or Demographics, Medical History, Baseline Characteristics, and Concomitant Medications)

Baseline and demographic characteristic variables (including date of birth, sex, race, ethnicity, and Fitzpatrick skin type) will be tabulated using descriptive statistics. For each continuous variable, the summary will include the mean, standard deviation, median, minimum and maximum. For each categorical variable, the summary will include frequencies and percentages.

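### The primary interval is valid, but it leaves out side allocation, the one factor the trial randomises, and may be slightly wider than needed

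*Protocol*

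**What the plan says.** Every subject receives both products, one in each nasolabial fold. What is randomised is the side. Protocol section 8.1: "The side of the face for each product will be randomly assigned". Section 8.4.2 adds: "The side of the face treated with either product will vary from subject to subject based on the randomization assignment made at Visit 1/Day 1". On method, 8.4.2 says "Randomization will be performed according to a computer-generated randomization scheme" and "No stratification based on age, sex, or other characteristics will be performed"; it states no rule for balancing sides.

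The primary variable is the change in WSRS from baseline to Week 24, compared as Restylane minus Revanesse, with non-inferiority claimed if the upper 95% limit is below 0.50. The synopsis says the interval for the difference between "treatments will be constructed using the paired t-test". Section 9.4 words it differently: "The 95% CI for difference between treatments will be constructed assuming a normal distribution of the change scores". Neither place mentions side of face.

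Section 8.4.3 describes a handed injection technique ("the dominant hand is used to inject filler", with the other hand applying traction). It also asks that technique and volume match on the two sides as far as possible.

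**The concern.** An injector keeps the same dominant hand for both folds, so a small left-right difference in result is conceivable. Where one exists, it enters the within-subject difference with a plus sign in one allocation group and a minus sign in the other. An analysis that pools the two groups treats that systematic part as noise. Analysing by the groups the trial has already randomised would remove it and keep the same estimand.

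What is at stake is the width of the interval that decides the non-inferiority claim. A second, smaller matter is wording: 9.4 refers to two treatment groups and to normality of the change scores, and does not repeat that the interval is paired.

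**Working it through.** **1. The plan's own figure.** Inputs from Protocol section 9.6: margin 0.50, true difference 0, SD of the within-subject difference 1.30, 85% power. Section 9.2 says "Two-sided hypothesis testing will be conducted for all tests", so the upper limit of a 95% interval is a one-sided test at 0.025.
- Normal approximation: n = (1.30 × (1.960 + 1.036) / 0.50)² = 60.7, so 61.
- Exact paired t: n = 63, power 0.852.

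The stated 63 at 85% is reproduced, and only as a paired calculation. Unpaired, the same inputs give 122 per arm.

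**2. Model with a side effect.** Let L be the left-minus-right difference in WSRS change under the same product, and θ the product effect (Restylane minus Revanesse). The within-subject difference is
- θ + L + error if Restylane is on the left,
- θ − L + error if Restylane is on the right.

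Pooling the groups gives a variance of about 1.30² + L² = 1.69 + L². With a side term the residual variance is 1.69.

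**3. Effect on the standard error.** The documents give no L; 0.2 to 0.4 grade is an assumption. The ratio of unadjusted to adjusted SE is √(1 + L²/1.69).

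| Assumed L | L²/1.69 | SE ratio | SE at n = 63 (1.300/√63 = 0.164 without L) |
|---|---|---|---|
| 0.1 | 0.6% | 1.003 | 0.164 |
| 0.2 | 2.4% | 1.012 | 0.166 |
| 0.4 | 9.5% | 1.046 | 0.171 |

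If 1.30 already contains the side effect, the ratio is √(1.69/(1.69 − L²)): 1.012 at L = 0.2 and 1.051 at L = 0.4. Either way the excess is about 1% to 5%.

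**4. False non-inferiority rate.** At a true difference of 0.50 the nominal rate is 0.025.
- Simple side randomisation, n = 63, 40,000 simulated trials per setting: the unadjusted interval gives 0.0246, 0.0253 and 0.0250 for L = 0.10, 0.25 and 0.50. The Monte Carlo error is √(0.025 × 0.975/40,000) = 0.0008, so all three agree with 0.025.
- Balanced sides: the estimate does not vary with L, but the pooled SE is too large by the ratio in step 3. The rate is about 1 − Φ(1.96 × ratio): 0.024 at L = 0.2 and 0.020 at L = 0.4, both below nominal.

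**5. Chance imbalance.** With n₁ and n₂ subjects in the two groups, the unadjusted estimate moves by L(n₁ − n₂)/n. Under simple randomisation this has mean zero and SD L/√n: 0.025 to 0.050 at n = 63, and 0.016 to 0.031 at n = 163, for L = 0.2 to 0.4. Its variance, L²/n, is exactly the extra term from step 2 divided by n. It is therefore the same quantity, already inside the paired-t standard error.

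**6. Power.** Simulated at n = 63 with simple randomisation:

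| Assumed L | Unadjusted | Side-adjusted |
|---|---|---|
| 0 | 0.852 | 0.844 |
| 0.10 | 0.847 | 0.843 |
| 0.25 | 0.842 | 0.849 |
| 0.50 | 0.804 | 0.848 |

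The adjustment loses slightly for L of 0.10 or less and gains above that. If all 163 subjects were evaluable, power is at least 0.99 with or without it, up to L = 0.50.

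**The case against.** The strongest reply is that nothing here is wrong. Side is randomised, so the mean within-subject difference is unbiased whatever L is, and the paired-t interval holds its level. That stands in full.

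A reader might infer that leaving side out raises the chance of a false non-inferiority claim. Step 4 shows that it does not: the rate stays at 0.025 or falls below it. A reader might also count the added variance and the imbalance shift as two separate harms. Step 5 shows that under simple randomisation they are one, and under balance there is no shift.

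The existence of L is also unsupported. The handed technique is a description, not evidence of a left-right difference at Week 24. The protocol works against one by asking for matching technique and volume and by treating each fold to optimal correction. This stands too, which is why the size can be given only as a range.

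A larger share could be obtained by assuming a smaller SD. The 1.30 is close to the root of the four summed variances in the section 9.6 table (0.42² + 0.79² + 0.50² + 0.81² = 1.7066, root 1.306), which allows for no within-subject correlation. But the documents give neither a correlation nor a smaller SD, so a larger figure cannot be rested on them. A smaller SD would also raise power and leave less at stake.

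Finally, section 9 leaves fuller methodology to an SAP that is not at hand and could add a side term. The protocol nonetheless names the primary interval, and as named it has none. On pairing, the synopsis and the sample size already settle the matter; the difference in 9.4 is one of wording and not a conflict of method.

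**Conclusion.** The planned primary interval is valid and unbiased. It does not use the side allocation, so any left-right difference is carried as noise. For an assumed L of 0.2 to 0.4 grade at SD 1.30, the standard error is about 1% to 5% larger than it need be, and the test is slightly conservative if sides are balanced. For L of about 0.1 or less there is no gain. At 63 per-protocol subjects the gain in power is under one point at L = 0.25 (0.849 − 0.842) and about four points at L = 0.50 (0.848 − 0.804). With most of the 163 evaluable it is negligible.

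This is an optional improvement. It rests on an assumed L and on the protocol's SD. It does not threaten the non-inferiority conclusion, and no stated figure is wrong.

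**What to change.** In section 9.4 and the synopsis, define the primary analysis along these lines: *the within-subject difference in WSRS change (Restylane minus Revanesse) is analysed in a linear model with side allocation (coded +1 or −1) as a factor; the product effect is the equally weighted mean of the two allocation groups, reported with its t-based 95% CI.* Keep the 0.50 limit and the decision rule as they are. Word 9.4 to match the synopsis, so that both say the interval is on paired within-subject differences.

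The cost is a sentence in each place and one degree of freedom. If sides are not balanced and L is zero, the equally weighted mean also loses a little precision: under one power point at n = 63 (0.852 to 0.844), and nothing visible at n = 163. The change should be made before unblinding.

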8.6.7 Wrinkle Severity Rating Scale (WSRS)

The WSRS Score is a 5-point scale with the following categories:

1. Absent - No visible fold; continuous skin line.
2. Mild - Shallow but visible fold with a slight indentation; minor facial feature; implant is expected to produce a slight improvement in appearance.
3. Moderate - Moderately deep folds; clear facial feature visible at normal appearance but not when stretched; excellent correction is expected from injectable implant.
4. Severe - Very long and deep folds; prominent facial feature; less than 2 mm visible when stretched; significant improvement is expected from injectable implant.
5. Extreme - Extremely deep and long folds, detrimental to facial appearance; 2 to 4 mm visible V-shaped fold when stretched; unlikely to have satisfactory correction with injectable implant alone.

The WSRS score will be assessed for each NLF at every study visit through Visit 6/Week 24 (Visit 1/Day 1, Visit 2/Week 1, Visit 3/Week 2, Visit 4/Week 4, Visit 5/Week 12, and Visit 6/Week 24 [End of Study/Early Termination for subjects who are not retreated]) by a blinded evaluator (blinded to the treatment assignment of each NLF). For subjects who are retreated, this will also be assessed at Visit 7/Week 28 and Visit 8/Week 52 (End of Study/Early Termination) but the evaluator does not need to be blinded for those assessments.

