9.6 Sample Size Determination

In a previous Prollinium split-face study of Revanesse Ultra versus Restylane, following were achieved with respect to the Investigator WSRS score:

	N	Revanesse (Mean \pm SD)	Restylane (Mean \pm SD)
WSRS Before Injection	110	3.22 \pm 0.42	3.20 \pm 0.50
WSRS at Month 6	110	2.34 \pm 0.79	2.41 \pm 0.81

From these statistics, the difference between Revanesse and Restylane (Restylane minus Revanesse) in change from baseline WSRS to Month 6 is estimated to have a mean value of -0.095 with an approximate standard deviation (SD) of 1.30.

Therefore, about 63 per-protocol (PP) subjects will supply a power of 85% with respect to change from baseline to Month 6 in WSRS score based on the following:

- The non-inferiority limit is 0.50. If the upper bound of the 95% confidence interval (CI) treatment difference (Comparator – Test) is less than 0.50 for the PP population, the Test product will be claimed to be non-inferior to the Comparator product.

- The difference between Comparator and Test (i.e., Comparator – Test) has a mean value of 0, with a standard deviation of 1.30.

A total of 163 subjects will be enrolled into the study to provide adequate data for monitoring the safety of the study product.

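### The primary paired analysis subtracts the between-fold baseline WSRS difference with a coefficient fixed at 1; estimating that coefficient would cost nothing and usually tighten the decisive limit

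*Protocol*

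**What the plan says.** The primary endpoint is change in WSRS from baseline to Week 24, taken for each fold. Section 9.4 of the protocol asks for summary statistics and a 95% CI "for the difference in change scores between the two treatment groups (Comparator minus Test product, i.e., Restylane minus Revanesse"). The method is then given as: "The 95% CI for difference between treatments will be constructed assuming a normal distribution of the change scores". The synopsis says that the interval for the difference between "treatments will be constructed using the paired t-test". No baseline covariate appears in either place.

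The decision rests on one limit: "If the upper bound of this 95% CI is less than the pre-specified non-inferiority (NI) limit (i.e. 0.50"), the test product is declared non-inferior.

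The baseline score of each fold is collected in any case. Section 8.6.7 states: "The WSRS score will be assessed for each NLF at every study visit through Visit 6/Week 24", and that schedule includes Day 1. Section 8.3.1 admits folds scoring 3 or 4, so a subject's two folds may differ by -1, 0 or +1 at entry. Section 8.4.2 randomises the side of the face and uses no stratification.

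Section 9.6 bases the sample size on a difference that "has a mean value of 0, with a standard deviation of 1.30" and concludes that "about 63 per-protocol (PP) subjects will supply a power of 85"%.

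**The concern.** The paired difference in change equals the between-fold difference at Week 24 combined with the between-fold difference at baseline, the latter with weight exactly 1. That weight is optimal only if one grade of baseline difference between the folds carries through, on average, as one full grade at Week 24. With a 5-point scale, a two-grade entry range and regression to the mean, a smaller slope is plausible. Part of the baseline difference then stays in the contrast as noise.

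Two things follow. The interval is wider than it needs to be. And if one product happens to be given the deeper folds, the estimate and its upper limit shift in a direction that can be seen from the baseline data. Since that upper limit alone decides the non-inferiority claim, both consequences bear on the decision criterion itself.

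**Working it through.** **Inputs from section 9.6 (earlier split-face study, N = 110).** Baseline SDs are 0.42 (Revanesse) and 0.50 (Restylane). Month 6 SDs are 0.79 and 0.81. Margin: "The non-inferiority limit is 0.50". Planned enrolment is 163.

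**Assumption.** r is the correlation between the between-fold difference at baseline and the between-fold difference at Week 24. The protocol does not give it, so a range is shown. Change is counted as improvement (baseline minus Week 24), the direction that gives section 9.6 its negative mean difference.

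**Step 1: reproduce the plan's figures.**
- SD: √(0.42² + 0.50² + 0.79² + 0.81²) = √1.7066 = 1.306. The planning SD of 1.30 therefore treats all four scores as uncorrelated.
- Sample size: a paired test with margin 0.50, SD 1.30, true difference 0 and one-sided 0.025 has power 85.2% at n = 63 by noncentral t (84.6% at n = 62). The stated 63 is confirmed as a paired calculation.

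**Step 2: variance with and without an estimated slope.** With zero correlation between folds:
- V0 (baseline difference) = 0.42² + 0.50² = 0.4264
- V1 (Week 24 difference) = 0.79² + 0.81² = 1.2802
- Unadjusted: V0 + V1 − 2r√(V0·V1)
- Adjusted: V1(1 − r²)
- Slope of the Week 24 difference on the baseline difference: r√(V1/V0), which equals 1 at r = √(0.4264/1.2802) = 0.577

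| r | Slope | SD unadjusted | SD adjusted | Variance saved | Power at n = 63, unadjusted / adjusted |
|---|---|---|---|---|---|
| 0 | 0 | 1.306 | 1.131 | 25% | 85% / 93% |
| 0.2 | 0.35 | 1.188 | 1.109 | 13% | 91% / 94% |
| 0.3 | 0.52 | 1.124 | 1.079 | 8% | 94% / 95% |
| 0.4 | 0.69 | 1.056 | 1.037 | 4% | 96% / 97% |
| 0.58 | 1.00 | 0.924 | 0.924 | 0% | 99% / 99% |

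The r = 0 row is the one that the planning SD implies. There, the n for 85% power falls from 64 (63 at the rounded SD of 1.30) to 48.

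**Step 3: dependence on the between-fold correlation.** If the two folds correlate equally at both visits (0 to 0.7 checked), the percentages hardly move. If the correlation differs by visit, they do:
- Baseline 0.7, Week 24 0.3: V0 = 0.4264 − 2(0.7)(0.42)(0.50) = 0.1324 and V1 = 1.2802 − 2(0.3)(0.79)(0.81) = 0.8963. The saving is 13% at r = 0 and 1% at r = 0.3.
- Baseline 0.3, Week 24 0.7: V0 = 0.3004 and V1 = 0.3843. The saving is 44% at r = 0 and 27% at r = 0.3.

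**Step 4: effect of chance imbalance.** A baseline imbalance of 1 SE shifts the unadjusted estimate by (1 − slope) × √(V0/n):
- n = 63: 0.08 grade at r = 0, 0.04 at r = 0.3, none at r = 0.58.
- n = 163: 0.05 at r = 0 and 0.025 at r = 0.3.

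With the true difference at the margin, simulation at n = 63 and r = 0 gives an overall one-sided error of 0.027 against 0.025 nominal. Among trials in which Revanesse is given the deeper folds by more than 1 SE (about 16% of trials), the false non-inferiority rate is 9.5% in that simulation. By a normal approximation it is 9.1% at r = 0, 6.8% at r = 0.2 and 5.7% at r = 0.3. In the opposite imbalance it is 0.1% to 0.7%. In that approximation the rates do not depend on n.

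**Step 5: effect at planned enrolment.** With SD 1.30 and all 163 analysed, unadjusted power is 99.8%. The CI half-width goes from 0.201 to 0.175 at r = 0, the case with no carry-through.

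**The case against.** The strongest reply is that nothing here is an error. Each fold's own baseline is subtracted, the side is randomised, and a paired t interval on change is a valid, pre-specified analysis with the right overall error rate. All of that stands. A reader might infer that the plan ignores baseline, or that its interval is biased. The documents support neither: the baseline difference is removed with weight 1, and any bias exists only conditionally on a chance imbalance, averaging out over randomisations.

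The size is also uncertain. The 25% figure belongs to the zero-correlation case, and the protocol gives neither r nor the between-fold correlations. Nor do the earlier study's baseline SDs fit this trial's entry rule fully: with scores of 3 or 4 only, a mean of 3.20 forces an SD of about √(0.2 × 0.8) = 0.40, not 0.50. Using 0.40 for that fold gives V0 = 0.42² + 0.40² = 0.3364 and a saving of 21% rather than 25% at r = 0.

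The effect on the decision is small too. Enrolment of 163 far exceeds the 63 needed, and the earlier study's mean baseline difference was only 3.22 − 3.20 = 0.02.

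It could be added that section 9 leaves fuller methodology to the statistical analysis plan, which is not at hand. That does not remove the point, because the protocol itself fixes the form of the primary interval. The absence of the word paired in section 9.4 is not a real ambiguity: the synopsis supplies it and the sample size reproduces only as a paired design.

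What survives is that the adjustment uses data already collected, costs one degree of freedom, and deals with the conditional error, which a larger sample does not.

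**Conclusion.** The point holds as a free improvement of optional priority, not as a defect in validity. The primary analysis imposes a baseline coefficient of 1 where it could estimate one. In large samples the estimated version is never less precise, and it takes out the shift in the upper limit caused by one product being given the deeper folds.

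The variance saving is about 25% at r = 0, the case that the planning SD of 1.30 implies. It falls to about 13%, 8%, 4% and 0% at assumed r of 0.2, 0.3, 0.4 and 0.58. These figures rest on the earlier study's SDs and on equal between-fold correlation at both visits; if that correlation differs by visit, the saving may be smaller or larger. With 163 enrolled the outcome is unlikely to turn on this, because unadjusted power already exceeds 99% under the plan's assumptions. It would matter mainly if the true difference lay near the margin and the baseline imbalance favoured one product.

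**What to change.** In section 9.4 and the synopsis, define the primary analysis as follows. For each subject, regress the within-subject difference in WSRS change (Restylane minus Revanesse) on the within-subject difference in baseline WSRS. Take the estimate at zero baseline difference and compare the upper limit of its 95% t interval with 0.50. Keep the simple paired t interval as a sensitivity analysis. State the direction of change in the same sentence and use it throughout, so that the upper-limit rule reads one way only.

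The margin and the quantity estimated stay the same, because randomising the side makes the expected baseline difference between products zero. The cost is one sentence in each place and one degree of freedom, with no new data and no change to the sample size. The change should be made before unblinding so that the covariate is pre-specified.
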